## **6. OBJECTIVES**

### **6.1. Primary Objective**

The primary objective of the study is to evaluate the safety and tolerability of repeated dosing of PH94B over a period of up to 12 months as assessed by documenting AEs, standard clinical measurements (physical examination, vital signs, clinical chemistry, hematology, suicidality, level of depression, and 12-lead electrocardiogram [ECG]), and withdrawal symptoms.

- To assess individuals' sub [REDACTED]
- [REDACTED] observed level of overall severity of the subject's SAD symptoms over [REDACTED]
- [REDACTED] of the subject's SAD [REDACTED]
- [REDACTED]
- [REDACTED]
- [REDACTED]
- [REDACTED]
- [REDACTED]

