#### **9.4.1 eDiary**

Subjects participating in the study will be instructed to record their use of PH94B in an eDiary application. The eDiary will be made available to subjects as an “application” to be downloaded and used on their smartphone or a similar device.

Subjects will be instructed to complete the eDiary at the end of each day even if zero doses are taken that day. They will be instructed to provide information on the number of doses they self-administered that day and the approximate time of each dose.

After the subject has completed the dosing section, the eDiary will prompt the subject to answer if they have experienced any health problems that day. If they answer yes, the subject is asked to write a brief summary text in the eDiary. The Investigator or a delegate will review these summary texts at each visit and determine whether they are to be recorded in the EDC system as AEs, with their severity, duration, and relationship to the study drug.

A nominal payment will be made to subjects for each day that they complete the eDiary. This will be made available to the subject at the end of the study.

At each study visit from Visit 3 through Visit 14, study staff will review the subject’s eDiary entries. Additional training on the use of the eDiary may be administered if necessary (see Section 9.4).

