#### **10.2.4 Visit 15 (Follow-up, 54 weeks ±3 Days)**

At Visit 15, subjects should return to the study site and the following assessments will be completed:

- Measure vital signs after the subject has rested for 5 minutes: seated systolic and diastolic blood pressure, heart rate, respiratory rate, and body temperature (°F)
- Administer C-SSRS (Since Last Visit)
- Complete PWC-20
- Review and record AEs

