#### **11.2.1 Assessment**

The Investigator is responsible for the detection and documentation of events meeting the criteria and definition of an AE or SAE described previously. At each visit, the subject will be allowed time to spontaneously report any issues since the last visit or evaluation. The Investigator will then monitor and/or ask about or evaluate AEs using nonleading questions, such as

- “How are you feeling?”
- “Have you experienced any issues since your last visit?”
- “Have you taken any new medications since your last visit?”

Any clinically relevant observations made during the visit will also be considered AEs.

In addition, the Investigator will review the eDiary summary text for health problems and determine whether they are to be recorded in the EDC system as AEs.

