8.1. Adverse Events

Treatment emergent AEs (TEAEs) are defined as:

- AEs with onset at the time of or following the start of treatment with IP through final Visit or follow-up phone call.
- AEs starting prior to the start of treatment with IP but increasing in severity or relationship at the time of, or following, the start of treatment with IP through Visit 14 (End of Treatment/Follow-Up).
- AEs that occur between Visit 14 and Visit 15.

Any medical condition that is present at the time that the subject is screened will be considered as baseline and not reported as an AE. However, if the study subject's condition deteriorates at any time during the study, it will be recorded as an AE.

The Investigator will record all reportable events with start dates occurring any time after informed consent is obtained until 7 days after the last day of study participation. Events will be followed for outcome information until resolution or stabilization. Missing and partially missing start dates will be imputed for the purpose of analysis as described in Section **Error! Reference source not found.**

All AEs, TEAEs, and serious AEs (SAEs) will be coded using the MedDRA dictionary, as discussed in Section **Error! Reference source not found.**

All AE data will be categorized as Severe > Moderate > Mild. Relationship of all AEs to IP will be categorized as related or not related. In the summaries showing severity and relationship to study drug, the event with the maximum severity or strongest relationship to study drug will be reported. If a particular event is missing the severity and/or relationship, then the strongest possible severity or relationship will be assumed for analysis (severity = severe, relationship = related).

An overall summary of TEAEs will be provided; this will present number and percent of subjects who reported at least 1 of the following: TEAE (including any TEAE, TEAEs by maximum severity, and related TEAEs), TEAE leading to discontinuation of the study drug, TEAE leading to discontinuation from the study, serious TEAEs, and SAEs leading to death. TEAEs will be summarized by two time periods (TEAEs which occur prior to Visit 14 and those that occur during or after Visit 14).

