In addition to the overall summary, summaries of the number and percentage of subjects with TEAEs will be displayed by overall by SOC and preferred term by time period. Summaries of TEAEs by severity (Severe > Moderate > Mild) and relationship to IP (Related > Not Related)

will also be provided. Serious TEAEs and TEAEs resulting in discontinuation of IP will be summarized separately in a similar manner.

Subject listings of AEs, SAEs, and AEs causing discontinuation of IP will be produced. Adverse events that are treatment emergent will be flagged.

The AE summary tables will include counts of subjects. Therefore, if a subject experiences more than 1 episode of a particular AE, the subject will be counted only once for that event. If a subject has more than 1 AE that is coded to the same preferred term, the subject will be counted only once for that preferred term. Similarly, if a subject has more than 1 AE within a SOC, the subject will be counted only once in that SOC. This will be handled separately for each time period (post-Visit 2 through Visit 15 [End of Treatment/Follow-up]).

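### The SAP's TEAE percentages before and from Visit 14 cannot be compared: the periods differ in length and in how AEs are found, and neither is cleanly on or off drug

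*SAP*

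**What the plan says.** SAP 8.1 divides the tabulation at Visit 14: "TEAEs will be summarized by two time periods (TEAEs which occur prior to Visit 14 and those that occur during or after Visit 14". The measure is a count and percentage of subjects: "summaries of the number and percentage of subjects with TEAEs will be displayed by overall by SOC and preferred term by time period". No rate per unit of time, no denominator specific to the second period and no note on AE sources is given. SAP 4.1 sets a general denominator of subjects in the study population with non-missing values.

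Protocol 9.4.1 describes a daily source of AE information: "the eDiary will prompt the subject to answer if they have experienced any health problems that day". Site staff decide from the free text whether an AE is recorded. The scheduled review is bounded: "At each study visit from Visit 3 through Visit 14, study staff will review the" subject's entries. For the follow-up visit, Protocol 10.2.4 says "At Visit 15, subjects should return to the study site and the following assessments will be completed" and then lists vital signs, C-SSRS, PWC-20 and AE review. Table 2-1 agrees: at Visit 15 it has no eDiary review, laboratory tests, ECG or physical examination.

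The general AE inquiry in Protocol 11.2.1 covers all visits: "At each visit, the subject will be allowed time to spontaneously report any issues since the last visit or evaluation". The diary is an addition to it: "the Investigator will review the eDiary summary text for health problems".

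The primary objective in Protocol 6.1 includes the documentation of AEs, standard clinical measurements "and withdrawal symptoms".

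**The concern.** A table with one column before Visit 14 and one from Visit 14 onward invites the reader to treat it as on drug against off drug. If the second percentage is much lower, the natural conclusion is that stopping the drug brings no excess of AEs. That matters because withdrawal is part of the primary objective. PWC-20 is the designated measure, but it has no assessment before Visit 14 and asks about the week after stopping, while Visit 15 falls about two weeks after the last dose. AEs after treatment are the main supporting evidence. If the columns differ for reasons unrelated to the drug, the table cannot give that support, and nothing in SAP 8.1 warns the reader.

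**Working it through.** The plan has no figure of its own to reproduce on this point. The sample size of up to 600 is set by reference to a guideline, and no AE rate is given.

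**Step 1: period lengths (Table 2-1).** Visit 14 is at 52 weeks = 364 days and Visit 15 at 54 weeks = 378 days. The periods are 364 and 378 − 364 = 14 days, a ratio of 364/14 = 26. With windows of ±14 and ±3 days, Visit 14 falls on days 350 to 378 and Visit 15 on days 375 to 381. Read literally, the gap runs from 375 − 378 = −3 to 381 − 350 = 31 days, so the second period also varies between subjects.

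**Step 2: AE sources (Table 2-1 with footnote c; Protocol 10.2.2 to 10.2.4).**

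| Source | Visits 3–13 | Visit 14 | Visit 15 |
|---|---|---|---|
| AE inquiry | yes | yes | yes |
| eDiary review | yes | yes | not listed |
| Laboratory tests, ECG | yes | yes | no |
| Physical examination | focused | comprehensive | no |
| Vital signs, C-SSRS | yes | yes | yes |
| PWC-20 | no | yes | yes |

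Protocol 11.1.1 and 13.1.4 allow abnormal laboratory, ECG and examination findings to count as AEs, so the loss of these after Visit 14 affects AE counts directly. In the other direction, a finding dated on the Visit 14 day enters the second column, and that visit has the comprehensive examination.

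**Step 3: on and off drug.** The second period includes Visit 14 itself. Under Protocol 7.1, subjects who stop early attend Visit 14 as soon as possible after stopping, so the off-drug days before that visit belong to the first column.

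**Step 4: effect of length, with assumed rates.** Let p be the share of subjects with a TEAE in 364 days (assumed), with a constant hazard, and let s be relative ascertainment after Visit 14 (assumed). The share expected in 14 days is 1 − (1 − p)^(14s/364) = 1 − (1 − p)^(s/26). Counts in brackets are per 600 subjects, all assumed to be followed.

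| p | s = 1.0 | s = 0.8 | s = 0.5 | s = 1.2 |
|---|---|---|---|---|
| 20% | 0.85% (5.1) | 0.68% (4.1) | 0.43% (2.6) | 1.02% (6.1) |
| 40% | 1.95% (11.7) | 1.56% (9.4) | 0.98% (5.9) | 2.33% (14.0) |
| 60% | 3.46% (20.8) | 2.78% (16.7) | 1.75% (10.5) | 4.14% (24.8) |
| 80% | 6.00% (36.0) | 4.83% (29.0) | 3.05% (18.3) | 7.16% (43.0) |

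At p = 40%, length alone removes 40 − 1.95 = 38.05 percentage points. Halving ascertainment removes a further 1.95 − 0.98 = 0.97. Even a true doubling of the hazard after stopping would show as 1 − 0.6^(2/26) = 3.85% beside 40%.

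**Step 5: what a rate does not solve.** Per patient-day, length cancels, but the change in hazard and s enter as a product. A doubling with s = 0.5 gives 2 × 0.5 = 1, which looks like no change. No change with s = 1.2 looks like a 20% rise. Sources must therefore be aligned or declared as well.

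**The case against.** A reader might infer that off-drug AEs must look rarer because the diary is no longer read. The documents do not support that:

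- The core inquiry continues at Visit 15, over a nominal two-week recall instead of about a month. PWC-20 adds 20 structured questions on withdrawal-type symptoms. The protocol does not say that PWC-20 answers feed AE records, so the offset is uncertain, but it cannot be set to zero.
- Events dated on the Visit 14 day, with its full examination, can raise the second column.
- The share of AEs found through the diary is not stated. SAP section 10 calls eDiary data unreliable. That remark concerns dosing patterns, but it limits the diary's value as a benchmark.
- Neither document says that diary entry stops at Visit 14. Protocol 9.4.1 also says, without an upper limit, that the health-problem texts are reviewed at each visit. This is an inconsistency within the section, not proof that review ends.

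It is also fair that Protocol 6.3 maps withdrawal to PWC-20, so the AE column is supporting evidence only. SAP section 8 plans no test between periods and nowhere claims equal ascertainment.

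These points defeat a claim about direction. They do not make the columns comparable, and the inequality of length needs no assumption about the diary.

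**Conclusion.** The point holds as one of comparability. Three facts rest on the documents alone: a nominal 26:1 ratio of period lengths shown as unadjusted percentages, AE sources that change at Visit 14, and periods that do not match on-drug and off-drug time. Length dominates: under a constant hazard, an assumed 40% becomes 1.95% (about 12 of 600) and an assumed 60% becomes 3.46% (about 21 of 600) with identical collection. The ascertainment difference is real, but its net direction and size cannot be determined, and no under-recording figure should be attached to it. What follows is that neither a rise, a fall nor no change in AEs after stopping can be read from the SAP 8.1 percentages. With counts this small, even a corrected comparison stays descriptive.

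**What to change.** **SAP 8.1**
- Define the off-drug period as running from the last dose, or from the end-of-treatment date where the last dose is not reliably known, to Visit 15. State to which period an event dated on the boundary day belongs.
- Use as denominator the subjects actually followed after that date.
- Report AEs per patient-day for that period against the same subjects' last 14 on-drug days. Because dosing is as needed, say that on-drug means within the treatment period.
- Footnote the difference in sources: eDiary review, laboratory tests, ECG and physical examination up to Visit 14; PWC-20 only at Visits 14 and 15.
- Reconcile the TEAE window. Protocol 13.1.4.1 ends it at the Follow-up or Early Termination Visit, whichever is first, while SAP 8.1 and Protocol 11.1.5 run on to follow-up.

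**Protocol**
- In 9.4.1, reconcile review at each visit with review at Visits 3 to 14.
- For subjects not yet past Visit 15, continue the daily health-problem question to that visit, and add eDiary review at Visit 15 to Table 2-1 and 10.2.4.

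**Cost.** The SAP changes need no new data. The protocol change adds about 14 nominal diary payments and a short review per subject, using an existing app and visit, and brings in data from a diary that the SAP calls unreliable for dosing patterns. SAP section 10 reads as written late in the study; if follow-up is complete, the SAP definitions, rates and footnote are what can still be done.

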STATISTICAL METHODS	
Analysis Populations:
 
Safety population: All subjects who receive IP.
 
All analyses will be performed using the Safety population.
 
Safety Analyses:
 
Safety and tolerability implications are best addressed by applying descriptive statistical methods to the data, supplemented by calculation of confidence intervals wherever this aids interpretation. The incidence of AEs for defined periods of exposure (e.g., 3 months, 6 months, 9 months, 12 months, and overall) will be evaluated in the form of a proportion relating number of subjects experiencing events to number of subjects at risk for AEs by organ, relatedness, severity of reported AE, and by frequency of AE. In addition, frequency-type of reported AEs (once, continuous, or adaptability to treatment) by time of occurrence after Visit 2 dispensation may be tabulated. These data will be summarized and tabulated, including confidence intervals when appropriate, for descriptive purposes, and may serve as nonparametric endpoints. Time series analysis will be used where warranted to determine whether frequency of AEs changes with increased duration of exposure.
 
Efficacy Analyses:
 
Exploratory endpoints address efficacy using patient- and clinician-rated scales and will be evaluated for significant changes from baseline using a generalized linear model for repeated measures.

SAMPLE SIZE DETERMINATION	
Based on feedback from the FDA, the sample size for this study (up to 600 subjects) has been selected to attain a PH94B safety database per the ICH E1 Guideline.

STUDY AND TREATMENT DURATION	
The sequence and maximum duration of the study periods will be as follows:
 
 
1. Screening and washout (if applicable): From 7 to 35 days
 
2. 12-Month treatment period: From Visit 2 (Baseline) through Visit 14 (End of Treatment)
 
3. Follow-up period: Follow-up visit (Visit 15) conducted approximately 2 weeks after last treatment
 
 
The maximum study duration for each subject is approximately 59 weeks.
 
The maximum treatment duration for each subject is 12 months.

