## 2.2. Schedule of Events

Table 2-1: Schedule of Events

Assessment/Evaluation	Study Periods					
	Visit 1	Visit 2	Visit 3	Visits 4 to 13	Visit 14 / ET	Visit 15
	Screening	Baseline	1st Month	Monthly	End of Treatment	Follow-up
	[REDACTED]	[REDACTED]	[REDACTED]	[REDACTED]	[REDACTED]	[REDACTED]
Informed Consent Form	X a	X a				
Subject Demographics	X					
Urine Drug Screen	X	X	X	X	X	
Pregnancy Test b	X	X	X	X	X	
MINI 7.0.2	X					
Medical and Psychiatric History	X					
Record Concomitant Medication Use	X	X	X	X	X	
[REDACTED]	[REDACTED]					
LSAS	X	X	X	X	X	
HAM-D17 [REDACTED]						
C-SSRS	X	X	X	X	X	X
Physical Examination c,d	X	X	X	X	X	
Vital Signs	X	X	X	X	X	X
12-Lead Electrocardiogram e	X	X	X	X	X	
Clinical Chemistry, Hematology, and Urinalysis	X	X	X	X	X	
Review Inclusion/Exclusion Criteria	X	X f				
CGI-S	X	X	X	X	X	
CGI-I			X	X	X	
PGI-C			X	X	X	
PWC-20					X	X

Assessment/Evaluation	Study Periods					
	Visit 1	Visit 2	Visit 3	Visits 4 to 13	Visit 14 / ET	Visit 15
	Screening	Baseline	1st Month	Monthly	End of Treatment	Follow-up
	Day -35 to Day -7	Day 0	Day 30 ±3 days	±7 days	52 Weeks ±2 weeks	54 Weeks ±3 days
Training on Use of PH94B		X				
Storage Instructions		X	X	X		
Training on eDiary App to Record PH94B Use and Health Problems		X				
Adverse Event Recording		X	X	X	X	X
Dispense PH94B to Subject		X	X	X		
eDiary Review			X	X	X	

Abbreviations: C-SSRS = Columbia-Suicide Severity Rating Scale; CGI-I = Clinical Global Impression Scale of Improvement; CGI-S = Clinical Global Impression Scale of Severity; eDiary = electronic diary; ET = Early Termination; HAM-A = Hamilton Rating Scale for Anxiety; HAM-D17 = Hamilton Rating Scale for Depression (17 items); LSAS = Liebowitz Social Anxiety Scale; MINI = Mini-International Neuropsychiatric Interview; PGI-C = Patient Global Impression of Change; PWC-20 = Penn Physician Withdrawal Checklist; SAD = social anxiety disorder

- a Subjects will sign an informed consent form for the present study at either Visit 1 or Visit 2, depending on when they enter the study.
- b Pregnancy tests will only be given to female subjects of childbearing potential and not post-menopausal females.

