Subjects will be instructed to return to the clinic for Visit 3 after 30 days ( $\pm 3$  days). At Visit 3, subjects will undergo clinical laboratory assessments (clinical chemistry, hematology, urinalysis, pregnancy test, and urine drug screening), vital signs, 12-lead ECG, physical examination (limited to nasal passage and oropharynx examination unless any AEs are reported), HAM-D17, [REDACTED] LSAS, C-SSRS, CGI-S, CGI-I, and self-evaluation by the patient-reported outcome measure, Patient Global Impression of Change (PGI-C). At Visit 3, PH94B use and any daily reports of health problems that have been recorded in the eDiary application will be reviewed and AEs and concomitant medications will be reported and recorded. Subjects will receive a 1-month supply of PH94B.

Subjects will return to the clinic at monthly intervals ( $\pm 7$  days, Visits 4 to 13), and will repeat the same assessments as those performed at Visit 3. PH94B use and any daily reports of health problems that have been recorded in the eDiary application will be reviewed, AEs and concomitant medications will be reported and recorded at each visit. Subjects will receive a 1-month supply of PH94B at each monthly visit.

At Visit 14 (12 months $\pm$ 2 weeks), treatment will conclude, and subjects will undergo clinical laboratory assessments (clinical chemistry, hematology, urinalysis, pregnancy test, and urine drug screening), vital signs, 12-lead ECG, physical examination, HAM-D17, [REDACTED] LSAS, C-SSRS CGI-S, CGI-I, PGI-C, and the Penn Physician Withdrawal Checklist (PWC-20). Also, PH94B use and any daily reports of health problems that have been recorded in the eDiary application will be reviewed, and AEs and concomitant medications will be recorded and reported. Subjects will also be informed of their follow-up visit (Visit 15).

Subjects will return to the clinic for a follow-up visit (Visit 15, 54 weeks  $\pm$ 3 days), approximately 2 weeks after the last PH94B administration, to undergo C-SSRS, PWC-20, and vital signs assessments, and record AEs.

Subjects who discontinue study treatment without completing 12 months of treatment will attend an Early Termination Visit (Visit 14) as soon as possible after discontinuing treatment, and return to the clinic for a follow-up visit (Visit 15) approximately 2 weeks later.

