### **13.1.3 Exposure and Compliance**

Investigational product administration will be summarized in terms of total number of doses received and average number of daily doses.

Descriptive statistics will be provided overall and for each 3-month period of exposure (0-3 months, 4-6 months, 7-9 months, and 10-12 months).

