### **13.1.4 Safety and Tolerability Analyses**

Safety analyses will be conducted using data from the safety population (as defined in [Section 13.1.1](#)). Safety variables include treatment-emergent AEs, clinical laboratory values, vital signs, changes in suicidality (C-SSRS), level of depression (HAM-D17), PWC-20 results, ECG readings, and physical examination results. No formal inferential analyses will be conducted for safety variables, unless otherwise noted.

The incidence of AEs for defined periods of exposure (e.g., 3 months, 6 months, 9 months, 12 months, and overall) will be evaluated in the form of a proportion relating number of subjects experiencing events to number of subjects at risk for AEs by organ, relatedness, severity of reported AE, and by frequency of AE. In addition, frequency-type of reported AEs (once, continuous, or adaptability to treatment) by time of occurrence after Visit 2 dispensation may be tabulated. These data will be summarized and tabulated, including CIs when appropriate, for descriptive purposes. Abnormal laboratory values, vital signs, 12-lead ECGs and findings from physical evaluations that are logged as AEs are included.

For each AE category (organ, relatedness, severity, frequency, etc.) the number of subjects reporting 1 or more AEs during the specified time period divided by the number of subjects exposed to the IP during that time period may serve as a nonparametric endpoint, and be subject to evaluation using time series analysis to investigate whether frequency of AEs changes with increased duration of exposure.

Descriptive statistics will be used to portray safety and tolerability of PH94B as measured by reports of AEs and SAEs, changes in laboratory values, 12-lead ECGs, physical examination, vital signs, and withdrawal symptoms.

Safety endpoints are as follows:

- Incidence and severity of AEs, AEs leading to discontinuation, and SAEs
- Changes in vital signs results
- Changes in clinical laboratory evaluation (hematology, chemistry, and urinalysis) results
- Changes in 12-lead ECG results
- Changes in physical examination findings
- Changes in HAM-D17 scores
- Changes in C-SSRS scores
- PWC-20 scores after termination of PH94B

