4.2. Interim Analysis and Data Monitoring

No interim analyses are planned.

5. Analysis Populations

The following analysis populations are planned for this study:

- **Safety Population:** All subjects who are dispensed IP during Visit 2 (Baseline) will be included in the Safety population. All subjects will receive PH94B in an open label fashion. Adverse events (AEs) will be grouped by associated length of exposure and level of PH94B use.

Inclusion of subjects in the Safety Population will be determined prior to database lock.

6. General Issues for Statistical Analysis

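### SAP 8.1 splits treatment-emergent adverse events only at Visit 14, so the incidence by exposure period set out in Protocol 13.1.4 and SAP 5 is not carried out, and SAP 10 does not clearly declare a change

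*SAP*

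**What the plan says.** **Protocol.** Section 13.1.4 makes a firm statement: "The incidence of AEs for defined periods of exposure (e.g., 3 months, 6 months, 9 months, 12 months, and overall) will be evaluated", as the proportion of subjects with events among subjects at risk. The cut-points are examples. The synopsis (2.1) gives the purpose: "Time series analysis will be used where warranted to determine whether frequency of AEs changes with increased duration of exposure". Section 13.1.3 already defines matching periods for dosing summaries, "for each 3-month period of exposure (0-3 months, 4-6 months, 7-9 months, and 10-12 months").

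**SAP 5 (Analysis Populations).** The grouping is repeated, with a second dimension added: "Adverse events (AEs) will be grouped by associated length of exposure and level of PH94B use".

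**SAP 8.1.** The rule actually specified is: "TEAEs will be summarized by two time periods (TEAEs which occur prior to Visit 14 and those that occur during or after Visit 14"). The next paragraph adds that "summaries of the number and percentage of subjects with TEAEs will be displayed by overall by SOC and preferred term by time period", but gives no further cut-points.

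**Visit 14.** The protocol schedule places it at "52 Weeks ±2 weeks", and the same visit serves as the early termination visit. Under Protocol 7.1, subjects who stop early "will attend an Early Termination Visit (Visit 14) as soon as possible after discontinuing treatment".

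**SAP 10.** The declared changes cover removed endpoints (not named), the COVID-19 questionnaire, the eDiary-based use-pattern objectives, the interim safety analysis, and a qualitative review of categorical data in place of change in proportion over time. None names adverse events by exposure period.

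**The concern.** The primary objective is safety and tolerability of repeated dosing for up to 12 months. With no control arm, the timing of onset is one of the few internal signals available. A reader will want to know whether events cluster in the first weeks, settle, or appear only with prolonged use.

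A split at Visit 14 separates on-treatment time from end of treatment and follow-up. It does not divide the treatment year. Nor is it a fixed exposure time: before Visit 14 may mean 2 months for one subject and 12 for another. A percentage over all treated subjects also dilutes late events, because those who have left can no longer contribute one. At stake is a prespecified summary that serves the primary objective. If it were produced later without being specified, SAP 1 would require it to be labelled post hoc.

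**Working it through.** The plan gives no figure on this point, and the sample size is set by reference to ICH E1 without a formula. There is nothing to reproduce. The check is a comparison of texts followed by an illustration.

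**1. Periods compared**

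| Source | Periods within treatment | Denominator |
|---|---|---|
| Protocol 13.1.4 | Several, e.g. to 3, 6, 9, 12 months, plus overall | Subjects at risk or exposed in the period |
| SAP 5 | By length of exposure; cut-points not given | Not given |
| SAP 8.1 | One (before Visit 14), then one from Visit 14 onward | No at-risk rule; SAP 4.1 default is the study population with non-missing values |

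SAP 8.1.1 and 8.1.2 use other period labels, but none is an interval within the treatment year.

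**2. Share of follow-up in the first SAP 8.1 period.** For a completer with Visit 14 at week 52 and Visit 15 at week 54: 52/54 = 96.3%.

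**3. Can the pooled row show a change with exposure?** *Assumptions:* 600 treated (the planned maximum). At-risk counts are interpolated linearly from 600 at month 0 through 300 at month 6 to 100 at month 12, giving 600, 450, 300 and 200 at months 0, 3, 6 and 9. The 300 and 100 are the interim triggers in Protocol 13.1.6, not a retention forecast. Event counts are chosen so that both patterns total 36. Each subject is counted once, at first onset. Intervals are Clopper-Pearson 95%.

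| Period (months) | At risk | Early pattern | Late pattern |
|---|---|---|---|
| 0-3 | 600 | 24 = 4.0% | 6 = 1.0% |
| 4-6 | 450 | 6 = 1.3% | 6 = 1.3% |
| 7-9 | 300 | 4 = 1.3% | 8 = 2.7% |
| 10-12 | 200 | 2 = 1.0% (0.1 to 3.6) | 16 = 8.0% (4.6 to 12.7) |
| Pooled | 600 | 36 = 6.0% (4.2 to 8.2) | 36 = 6.0% (4.2 to 8.2) |

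The pooled row is identical. If 300 or 100 were at risk in months 10-12, the late figure would be 16/300 = 5.3% (3.1 to 8.5) or 16/100 = 16.0% (9.4 to 24.7).

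**4. Effect of the denominator alone.** Take 5 subjects with a late-onset event (assumed):

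- 5/600 = 0.83% (0.27 to 1.93)
- 5/300 = 1.67% (0.54 to 3.85)
- 5/100 = 5.0% (1.64 to 11.28)

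Relative to all treated, the figure rises by 600/300 = 2 times or 600/100 = 6 times.

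**5. Would the SAP's date rules distort a period table?** Under SAP 6.1.8, an onset with a missing month goes to the month of first dose, or to the following month if that would precede first dose. An onset missing both month and day also goes to the month of first dose. Every such event would land in 0-3 months, whenever it occurred. A missing day alone shifts the onset by less than a month.

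**The case against.** **SAP 5 keeps the commitment.** This stands. A reader might infer that the SAP has abandoned analysis by exposure. The documents do not support that: SAP 5 still promises the grouping. What fails is the execution, because 8.1 sets a concrete two-period rule that does not implement it.

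**The table list proves nothing.** This stands too. No title in SAP 12.3 names an exposure period, but none names the Visit 14 split either, although 8.1 requires it. The table shells are not in the text available for review, so column layouts cannot be checked. The point rests on the wording of 8.1.

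**SAP 10 may already cover it.** The sentence on change in proportion over time is not limited to efficacy, and adverse event incidence is a proportion. Its wording resembles the CGI and PGI-C endpoints of SAP 2.2.2, but SAP 7.5 still plans those proportions by visit, so assigning it to them alone is inference. A reader might infer that the change was concealed. The text supports only that no change is clearly declared. The eDiary sentence could explain dropping level of use. It cannot explain dropping length of exposure, which needs only onset and visit dates.

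**The protocol wording is soft.** In part: the cut-points are examples, the time series step is optional, and Protocol 13.1.4.1 lists AE tables without exposure periods. The commitment to evaluate incidence by some set of periods is still firm.

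**The illustration is constructed.** It is. The event counts are invented, the at-risk counts borrow triggers for an interim analysis that SAP 10 removed, and 600 is a ceiling. It counts first onsets only, whereas the proposed table counts subjects with any event in a period. It shows what pooling can hide and predicts nothing.

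**The table is recoverable.** True. Start dates are recorded, listings are planned, and disposition is tabulated by duration. No data are lost.

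**Conclusion.** The point holds as a gap between a stated commitment and a stated rule. SAP 8.1 pools essentially all on-treatment time, 52 of 54 weeks (96%) for a completer. It therefore cannot show whether adverse event incidence changes with longer exposure, which Protocol 13.1.4 and the synopsis set out to examine. SAP 10 leaves the reader unsure whether this was intended.

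The text comparison needs no numerical assumption. It assumes only that the unseen shells follow 8.1. The size of any masking is unknown: the contrast between 1.0% and 8.0% behind a common 6.0% depends entirely on assumed counts. Nothing here suggests that a late safety signal exists or that the study would miss one. The change should be made because the analysis serves the primary objective and costs little.

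**What to change.** 1. **Add one TEAE table to SAP 8.1** and list it in 12.3: subjects with at least one event (n, %, 95% CI), overall and by SOC and preferred term, for 0-3, 4-6, 7-9 and 10-12 months. Count time from Visit 2, which is where SAP 6.1.7 starts exposure, and state the boundaries in days. The denominator is subjects still on treatment at the start of each period. Keep the existing period for events during or after Visit 14.
2. **Set a date rule for this table.** Do not use the SAP 6.1.8 imputation for onsets with a missing month. Show them in a row for unknown onset period, or assign them from the visit interval in which they were reported.
3. **Settle level of use.** Either group it from vial weights, since SAP 10 calls the eDiary data unreliable, or state in SAP 10 that this grouping is dropped. Correct SAP 5 to match.
4. **If the exposure-period table will not be produced,** say so in SAP 10 with the reason, naming adverse events, and amend SAP 5.

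The cost is one more descriptive table and a few sentences, using AE records already collected. Late periods may be sparse: with 100 at risk and no events, the upper 95% limit is still 3.6%. The interval shows that imprecision openly.
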